# High vs. Standard Dose Flu Vaccine in Adult Stem Cell Transplant Recipients: DMID Protocol Number 17-0085

Protocol version 6.0

Date: August 12, 2019

Table 3.	Screening Period	Visit 1	electronic communication	Optional Visit	Visit 2	electronic communication	Optional Visit	Visit 3	Influenza Season	Visit 4 Optional for repeaters for 2019-2020	June 30th
Days		0	1-3 and 8-10* days after visit 1	5-10 days after visit 1	28-42 days	1-3 and 8-10* days after visit 2	5-10 days after visit 2	28-42 days after visit 2		180 ±56 days after visit 3	Day 0 until June 30th
Consent	X	X									
Inclusion/exclusion		X			X						
Physical examination#, oral temperature		X			X						
Peripheral venipuncture or via central line		X		X	X		X	X		X	
HAI, NAI, and microneutralization assay		X**			X**			X**		X**	
B/T cell responses		X		X	X		X	X		X	
CBC d/p#		X			X			X		X	
Quantitative CD4, and CD8, CD19#		X			X			X		X	
Quantitative serum IgG and IgM#		X			X			X		X	
Study vaccine administration (HD-TIV or SD-QIV)		X			X						
Memory aid review			X			X					
Adverse event assessment		X	X	X	X	X	X				
Concomitant medication collection		X	X	X	X	X	X	X			
Immunizations reviewed		X			X			X		X	
telephone and/or electronic communication electronic communication			X			X			Weekly		
Pregnancy Test (if applicable)		X			X						
Collection of Nasal Swab for PCR testing for Influenza and other respiratory viruses ***		X		X	X		X	X		X	X
Proven clinical influenza illness review ##		X	X	X	X	X	X	X	X	X	X

\*8-10 telephone and/or electronic communication not required if the subject is seen at the optional visit within this window period;

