### b. Secondary Objectives:

- i. To determine whether HD-TIV compared with SD-QIV will increase the probability of achieving a  $\geq 4$ -fold rise in HAI titers,  $\geq 1:40$  HAI titer, or higher GMT titers to influenza B antigens in adult HSCT recipients.
- ii. To determine the frequency and severity of solicited local injection site adverse events (e.g. pain/ tenderness, redness, and swelling/induration at injection site) with HD-TIV compared to SD-QIV in adult HSCT recipients.
- iii. To determine the frequency and severity of solicited systemic adverse events (e.g. fevers, headache, fatigue/malaise, nausea, body ache/myalgia, general activity level, and vomiting) with HD-TIV compared to SD-QIV in adult HSCT recipients.
- iv. To define the relationship between HAI titers, *in vivo* T and B cell phenotype, and *in vitro* influenza-specific T and B cell response in adult HSCT recipients receiving either HD-TIV or SD-QIV.
- v. To correlate HAI responses to MN responses.
- vi. To compare the persistent HAI and MN titers for all four antigen seven months after the last vaccine dose to assess for persistence of antibody titers.
- vii. To compare influenza detection by PCR during influenza season in adult HSCT recipients receiving either HD-TIV or SD-QIV.
- viii. To assess HAI and MN response in patients (e.g. repeaters) undergoing two-consecutive years revaccination using the same antigen dose
- ix. To correlate HAI responses to neuraminidase inhibition titers (NAI).

**3. Study Area:** The study will be conducted in the Oncology Units or Clinics, or Clinical Trial Centers at the following sites: **Table 2** includes the yearly average number of transplants per site.

Table 2. Clinical Sites	Average Number of Yearly Allogeneic Transplants
Northwestern University Feinberg School of Medicine	167
Fred Hutchinson Cancer Research Center	300
University Hospital, University of Alabama at Birmingham	90
Vanderbilt University Medical Center	108
TOTAL	665

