# If these tests/procedures are performed as standard of care prior to enrollment, but on same calendar day of vaccination, they will not need to be repeated and these data can be collected as part of study information.

\*\*a second blood draw will be obtained post-IVIG/SCIG if IVIG/SCIG is administered at this visit.

\*\*\* Study staff will attempt to collect nose swabs from symptomatic patients throughout the study period.

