#### **May occur for further evaluations of AEs/SAEs.**

- Review current health status since the last visit.
- Memory aid will be reviewed if the unscheduled visit occurs within 7 days of vaccination.
- All concomitant medications will be recorded if the early termination occurs within 28 days of vaccination.
- A targeted physical examination and vital signs may be performed, as indicated.

**Early Termination Visit:** Subject Withdrawal Criteria: Subjects have the right to withdraw from the study at any time.

**Events Which Warrant Withdrawal:** The investigator may drop/withdraw a subject from the study if deemed appropriate. Criteria for termination of a subject include: lost to follow-up, non-compliance with the protocol, and/or clinically significant adverse events (e.g., immediate allergic reaction to vaccine, severe or anaphylactic in type), which constitute contraindications to further vaccine administration.

**Data Collection for Withdrawn Subjects:** Every attempt should be made to collect all data specified by the protocol relative to study vaccine received, including post-immunization blood samples.

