**Visit 4: 180 Days  $\pm$ 56 after Visit 3:**

- Approximately 30-60 mL of blood will be collected for HAI and MN assays to influenza virus antigens, phenotypic B, and T cell responses, B and T cell specific influenza responses, CBC d/p, quantitative CD4+/CD8+/CD19+ levels, and quantitative serum IgG and IgM concentrations.
- A nasal swab will be obtained, regardless of symptoms.
- For 2019-2020 enrollment season, visit 4 will be optional and subjects who volunteer to participate will have the procedures mentioned above completed.
- Note: For subjects who finish their visit 4 before the end of the flu season, influenza surveillance will continue until the end of the flu season at their site.

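### IVIG/SCIG and new immunosuppression between Visit 3 and Visit 4 are not scheduled to be recorded, although the Visit 4 titre is the endpoint of secondary objective vi

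*Combined protocol and SAP*

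**What the plan says.** - **Schedule.** In Table 3 the row "Concomitant medication collection" is marked at Visit 1, Visit 2, Visit 3, the post-vaccination contacts and the optional visits. It is blank for the influenza season, Visit 4 and June 30th.
- **Visit 4 procedures.** Section C.14 lists blood ("Approximately 30-60 mL of blood will be collected for HAI and MN assays to influenza virus antigens", plus cell counts and IgG/IgM) and a nasal swab. No medication or history item appears. Table 3 does schedule immunization review and proven-influenza review at Visit 4.
- **Use of the Visit 4 serum.** Secondary objective vi is: "To compare the persistent HAI and MN titers for all four antigen seven months after the last vaccine dose".
- **IVIG/SCIG provision at Visit 4.** The Table 3 footnote reads: "a second blood draw will be obtained post-IVIG/SCIG if IVIG/SCIG is administered at this visit".
- **IVIG/SCIG elsewhere.** Receipt less than 28 days before vaccination is an exclusion for new subjects and for repeaters (Section C.4). No corresponding interval is set before the Visit 4 serum.
- **General data list.** Section C.6 includes post-transplant immunosuppressive medications (d), IVIG/SCIG history since transplant (h) and medications (s), with no visit or end date.
- **Unscheduled visits.** Section C.13 ties recording to vaccination: "All concomitant medications will be recorded if the early termination occurs within 28 days of vaccination".
- **Analysis.** Section C.17.b describes titres after one and two vaccine doses. It names no Visit 4 analysis and has no IVIG/SCIG or immunosuppression covariate.

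**The concern.** Donor antibody infused shortly before Visit 4 is measured by the same assays as vaccine-induced antibody. The plan recognises this around vaccination, through the 28-day exclusion and the extra sera when IVIG/SCIG is given at a visit. It makes no such provision for a dose given days or weeks before the persistence sample. A site that follows Table 3 captures two other events that can change the Visit 4 titre, a further vaccine and proven influenza, but is not prompted to ask about IVIG/SCIG or newly started systemic immunosuppression.

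What is at stake is the reading of objective vi. Passive antibody would make titres look more durable than the vaccine made them in either arm, and would shrink the difference between arms.

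**Working it through.** **1. The unscheduled interval.** Visit 3 is "28-42 days after visit 2", when dose 2 is given. Visit 4 is "180 ±56 days after visit 3".

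- Visit 3 to Visit 4: 180 − 56 = 124 days to 180 + 56 = 236 days.
- Dose 2 to Visit 4: 28 + 124 = 152 days to 42 + 236 = 278 days. At 30.44 days per month this is 5.0 to 9.1 months. The nominal value is (35 + 180)/30.44 = 7.1 months. This reproduces the plan's seven months and the 5-9 months in Section C.15.e.
- Share of the time from dose 2 to Visit 4 with no scheduled medication collection: from 124/(42 + 124) = 75% to 236/(28 + 236) = 89%.
- The interval holds 124/28 = 4.4 to 236/28 = 8.4 periods of 28 days.

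**2. Table against text.** The visit lists in Section C.14 are not exhaustive: the Visit 3 list also omits medications, yet Table 3 marks them there. The Visit 4 list alone would prove little. The point rests on both places being silent for Visit 4.

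**3. Illustrative size.** The documents give no IVIG/SCIG rate after Visit 3, no passive titre and no expected Visit 4 rate. The following are therefore assumptions:

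- true proportions with titre ≥1:40 at Visit 4 of 40% (HD-TIV) and 20% (SD-QIV);
- 55 evaluable per arm, the design figure in Section C.17.a;
- a share g of subjects in each arm exposed shortly before Visit 4, unrelated to their own response;
- a probability c that an exposed subject otherwise below 1:40 tests at or above it.

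Observed proportion = p + (1 − p)·g·c, so the difference between arms shrinks by the factor (1 − g·c). For g = 10% and c = 1: HD-TIV 0.40 + 0.60 × 0.10 = 46%; SD-QIV 0.20 + 0.80 × 0.10 = 28%; difference 18 points instead of 20.

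Power is by exact enumeration of a two-sided 5% two-proportion test. The last column removes exposed subjects, leaving 50, 44 and 38 per arm at 40% versus 20%.

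| g | Observed, c = 1 | Power, c = 1 | Power, c = 0.5 | Power, exposed removed |
|---|---|---|---|---|
| 0 | 40% v 20% | 64% | 64% | – |
| 10% | 46% v 28% | 51% | 58% | 60% |
| 20% | 52% v 36% | 38% | 51% | 55% |
| 30% | 58% v 44% | 30% | 44% | 49% |

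With the design rates of 50% versus 25% and c = 1, power is 79% at g = 0, then 66%, 54% and 45%. The direction does not depend on the rates chosen.

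**4. Chance imbalance.** The SD of the between-arm difference in exposure is √(2g(1 − g)/55): about 6 points at g = 10% and 9 points at g = 30%.

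**The case against.** **The documents are unclear rather than silent.** Section C.6 lists IVIG/SCIG history and medications with no end date, and Section C.1 calls for extra sera if IVIG/SCIG is received during any visit. Repeaters have prior and concomitant medications recorded at the next season's Visit 1, which may be the same day as Visit 4, and are checked for IVIG/SCIG in the previous 28 days. This stands against any claim that the exposure goes unrecorded. It does not close the gap: no collection point is set after Visit 3, only re-enrolling subjects are asked again, and no look-back period is stated for that question.

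**A reader might infer that passive antibody cannot be separated from vaccine persistence, or that no later analysis could deal with it.** The documents do not support that. Exposure can be abstracted from charts, and Visit 4 IgG and CD19 are partial markers, although total IgG does not distinguish infused from endogenous antibody.

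**A reader might also infer bias in favour of one arm.** Allocation is 1:1 and blinded, so later treatment should be similar on average. The expected effects are dilution and inflated within-arm persistence, with chance imbalance on top.

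**The power figures are not plan quantities.** Section C.17.b is Bayesian and specifies no Visit 4 test. They are only a yardstick. Removing exposed subjects also costs sample: the gain is about 2 to 5 points if half of the exposed become passively positive, and 9 to 19 points if all do. That supports a sensitivity analysis rather than a new main estimate, more so because the exclusion is post-randomization.

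**Reach is limited.** Objective vi is one of nine secondary objectives, new subjects come from the 2017-18 and 2018-19 seasons, and Visit 4 is optional in 2019-2020. This stands, and makes chart abstraction an important part of the remedy.

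**Conclusion.** The concern holds in a limited form. As scheduled, IVIG/SCIG and new systemic immunosuppression in the 124 to 236 days before the Visit 4 serum have no collection point, and the footnoted second draw handles only same-visit IVIG/SCIG. Passive antibody from an earlier dose can inflate within-arm persistence and dilute the arm contrast in objective vi.

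The size cannot be known from the documents. Under the stated assumptions, 10% exposure lowers power from 64% to between 51% and 58% and raises the SD-QIV proportion from 20% to as much as 28%. The effect of new immunosuppression on the titre has not been quantified.

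The primary objective, its post-dose titres and the sample size are unaffected. A reader might extend the point to the PCR comparison in objective vii through unrecorded antiviral use. The documents give no basis for that: weekly season contacts, ILI swabs and proven-influenza review continue after Visit 3.

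**What to change.** 1. In Table 3 and the Section C.14 Visit 4 list, add collection at Visit 4 of IVIG/SCIG (with dates) and systemic immunosuppressive or B-cell-depleting therapy since Visit 3. State in Section C.6 when items d, h and s are updated.
2. Abstract the same items from the chart for Visit 4s already completed, before the Visit 4 titres are analysed.
3. In Section C.17, specify the objective vi analysis for all subjects, with a sensitivity analysis that excludes or flags Visit 4 titres following IVIG/SCIG in the preceding 28 days. That interval is the plan's own pre-vaccination one. The documents do not show that it is long enough to clear passive HAI antibody, so a longer window can be shown beside it.

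The cost is a short CRF item at an existing visit, some chart abstraction, and fewer subjects in the sensitivity analysis. Treatment, visits and sample size do not change.

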# If these tests/procedures are performed as standard of care prior to enrollment, but on same calendar day of vaccination, they will not need to be repeated and these data can be collected as part of study information.

\*\*a second blood draw will be obtained post-IVIG/SCIG if IVIG/SCIG is administered at this visit.

\*\*\* Study staff will attempt to collect nose swabs from symptomatic patients throughout the study period.

## Proven clinical influenza illness is any breakthrough influenza illness confirmed by laboratory testing (ie Rapid antigen assay, PCR, virus culture, etc.)

## 5. Treatment Groups:

There will be two groups – HD-TIV versus SD-QIV. The subjects will be randomized in a 1:1 HD-TIV versus SD-QIV.

Treatment Group	Target Total N
Group 1 0.5 mL HD-TIV	69
Group 2 0.5 mL SD-QIV	69

**a. Randomization:** Subjects will be randomized 1:1 to either HD-TIV or SD-QIV. Randomization will be frequency-matched within each site to ensure balance between the groups and will be implemented using the Randomization Module within Vanderbilt's Research Electronic Data Capture (REDCap) database. The investigational pharmacy at each of the 4 institutions will distribute the assigned study vaccine. Because we are evaluating the immunogenicity of early timing of influenza vaccine post-transplant, we will limit enrollment to 42 (30%) subjects to  $\geq 12$  months post-transplant.

### For block randomization

1. For subjects 12-23 months since transplant, we will do block randomization on the following question: "Is the subject currently being treated for GVHD with systemic steroids?" (yes/no); if yes, they will be evenly distributed for randomization.
2. For subjects 3-11 months since transplant, block randomization will be on the following question: "Is the subject currently being treated for GVHD with systemic steroids or does the subject fall into one or more the following criteria: history of campath (alemtuzumab); history of anti-thymocyte globulin (ATG); cord transplant; haploidentical transplant; or post-transplant cytoxan (cyclophosphamide)?"
3. **Repeaters will retain their randomization number given from their initial enrollment and will not be re-randomized.**

**b. Enrollment:** Subjects will be enrolled from the Oncology units or clinics or clinical research centers at each institution. The healthcare team will help identify individuals who are eligible and will ask permission to be approached about the study. The research team will inform the subjects of the study and its procedures. Consent will be given to them to review. Ample time will be given to explain the study and answer any questions prior to signing the consent.

## 6. Data Collection:

The following information will be collected from each subject but not limited to:

- a. Type of transplant: (Bone marrow, peripheral blood, both bone marrow and peripheral blood, cord blood [single or double] or cord blood and peripheral blood; type of HSCT (HLA-identical sibling, HLA-mismatched relative, unrelated)
- b. Underlying disease and underlying disease risk
- c. Transplant cell dose
- d. Transplant conditioning regimen and post-transplant immunosuppressive medications
- e. History of acute or chronic GVHD
- f. GVHD grade
- g. HLA match
- h. History of IVIG/SCIG administration since transplant
- i. Chimerism status
- j. Gender (patient/donor gender)
- k. Race/ethnicity
- l. Age
- m. Social History (work, marital status, , etc.)
- n. Smoking History (is the subject exposed to secondhand cigarette/cigar/e-cigarette smoke)

- o. Household members (# people live in the subject's primary household as of date of visit-1, # of children less than 18 years , # of adults )
- p. History of influenza vaccination (pre and post-transplant)
- q. Past medical history
- r. CMV status (donor/recipient) and CMV viral end points
- s. Medications

## 7. Reporting Adverse Events:

The investigator is responsible for reporting:

- Any Grade 3 Adverse event that is not attributable to underlying disease for which the transplant was undertaken, **or** not attributable to GVHD, **or** not attributable to complications of immunosuppressive medications that are observed or reported through 7 days following vaccination (Day 0 through Day 7), regardless of their relationship to study product.
- Any other AE will not be reported unless it meets the SAE criteria (see Section 16.f).

Initial vaccine reactions will be assessed for at least 15 minutes after each vaccination. Subjects will be asked to record both solicited vaccine reactions and any unsolicited AEs on a memory aid for 7+ days after each vaccination (Day 0 through Day 7). Study personnel will attempt to contact the subjects by telephone and/or electronic communication at 1-3 days and 8-10 days after vaccination to review any AEs and SAEs. Adverse events and SAEs will be collected through 7 days following vaccination.

**Solicited systemic AEs** will be collected for 7+ days post each vaccination and will include the following: fevers, headache, fatigue/malaise, nausea, body ache/myalgia, general activity level, and vomiting. **Solicited injection site AEs** will include the following: pain, tenderness, redness/erythema, and swelling/induration at injection site.

**Reporting of Deviations:** All deviations will be reported to the Institutional Review Board (IRB) at the time of annual continuing review. Note: if the deviation affects patient safety and/or risk, the event will be reported immediately.

## 8. Study Withdrawal / Discontinuation:

### a. Reasons for Withdrawal or Discontinuation of Study Product

1. Subjects will be able to withdraw from the study at any time point.
2. A study subject will be discontinued from participation in the study if the following occur:
  - a. Any clinical adverse event (AE), laboratory abnormality, intercurrent illness, or other medical condition or situation occurs such that continued participation in the study would not be in the best interest of the subject. However, the subject may continue to be followed for safety purposes.
  - b. Development of any exclusion criteria may be cause for discontinuation from the study
  - c. Subjects may be removed from the study for failure to make follow-up visits.
  - d. Subjects may be removed from the study if new information becomes available that makes further participation unsafe.

### b. Handling of Withdrawals

Every attempt should be made to collect all data specified by the protocol relative to study vaccine received, including post-immunization blood samples. AEs will be followed to adequate resolution or until considered stable.

## 9. Follow-up Record Retention:

No follow-up visits are needed once the study is completed. A copy of the paper records will be retained for at least 7 years after completion of the study. The information stored in the OnCore and/or REDCap database will be kept indefinitely. The samples (blood) collected will be labeled with the same numeral ID and stored in in the Vanderbilt University Medical Center. With the permission of the subjects any leftover samples will be kept and used for future research and will be stored at Vanderbilt University Medical Center. A separate IRB approval will be sought prior to the use of these samples.

## 10. Investigational Product and Risk Information:

Fluzone Quadrivalent® is a Federal Drug Administration (FDA)-approved vaccine and is recommended for all patients ≥6 months.

Fluzone® HD-TIV has not yet been approved for individuals <65 years of age. The current seasonal influenza vaccine will be used throughout the entire study.

- a. **Acquisition:** Fluzone Quadrivalent® and Fluzone® HD, preservative free, licensed product formulated for the 2017-2018, 2018/2019, and/or 2019/2020 influenza season will be donated by Sanofi Pasteur and distributed to each site of the 4 institutions.
- b. **Formulation, Packaging, and Labeling:** Fluzone Quadrivalent® and Fluzone® HD, preservative free, licensed product, Sanofi Pasteur, Swiftwater, PA. The 2017-2018 influenza strain recommendations are the following: A/Michigan/45/2015 (H1N1)-like virus; an A/Hong Kong/4801/2014 (H3N2)-like virus; and a B/Brisbane/60/2008-like virus (this is a B/Victoria lineage virus) for both HD-TIV and SD-QIV; and in Fluzone Quadrivalent®, additional B virus, B/Phuket/3073/2013-like virus (this is a B/Yamagata lineage virus). The Fluzone package inserts for the 2017-2018 influenza season for both vaccines will be available in the Protocol Library.
- c. Fluzone Quadrivalent® and Fluzone® HD, preservative free, licensed product formulated for the 2018-2019 influenza season, Sanofi Pasteur, Swiftwater, PA will be obtained. Formulation, Packaging, and Labeling: Fluzone Quadrivalent® and Fluzone® HD, preservative free, licensed product, Sanofi Pasteur, Swiftwater, PA. The 2018-2019 recommendations are the following: A/Michigan/45/2015 (H1N1)pdm09-like virus; an A/Singapore/INFIMH-16-0019/2016 (H3N2)-like virus; and a B/Colorado/06/2017-like virus (this is a B/ Victoria lineage virus); and in Fluzone Quadrivalent®, additional B virus, B/Phuket/3073/2013-like virus, (this is a B/ Yamagata lineage virus). The Fluzone package inserts for the 2018-2019 influenza season for both vaccines will be available in the Protocol Library.
- d. The 2019-2020 influenza strain recommendations are the following: A/Brisbane/02/2018 (H1N1)pdm09-like virus; A/Kansas/14/2017 (H3N2)-like virus; and B/Colorado/06/2017-like virus (B/Victoria/2/87 lineage) for both HD-TIV and SD-QIV; and in Fluzone Quadrivalent®, additional B virus, B/Phuket/3073/2013-like virus (B/Yamagata lineage). The Fluzone package inserts for the 2019-2020 influenza season for both vaccines will be available in the Protocol Library.

**c. Product Storage and Stability:** The vaccine will be stored in the original package to protect from light. The vaccine will be stored in secure, limited-access, temperature-monitored refrigerator environments at 2°C to 8°C (35.6°F to 46.4°F) until needed. The temperature of the storage unit will be monitored for the duration of the trial, and documentation of proper dedicated storage will be maintained. It will not be frozen. In the event of accidental deep-freezing or disruption of the cold chain, vaccines will not be administered.

**d. Dosage, Preparation and Administration of Study Intervention/ Investigational Product:** Either dose (0.5 ml) of SD-QIV or HD-TIV (Fluzone Quadrivalent®, Sanofi Pasteur or Fluzone® HD-TIV, Sanofi Pasteur) will be administered intramuscularly in either the right or left arm. In preparing either vaccine, the pre-filled syringe will be gently shaken and visually inspected for particulate matter and/or discoloration prior to administration (the SD-QIV/HD-TIV may normally be clear to slightly opalescent). If either condition exists, the pre-filled syringe will not be used.

Subjects are randomized in a 1:1 fashion to receive either 2 doses of 0.5ml of HD-TIV (60µg of each influenza antigen) or 2 doses of SD-QIV (15 µg of each influenza antigen) of the current seasonal influenza vaccine (e.g. 2017-2018 or 2018/2019), 28-42 days apart. The repeaters retain their randomization code.

Each of these study products will be labeled according to manufacturer specifications and include the statement “Caution: New Drug-Limited by Federal Law to Investigational Use”.

**e. Modification of Study Intervention/Investigational Product for a Participant:** No dose modifications will be allowed.

**11. Side Effects with Influenza Vaccination.** The side effects listed in the package insert include:

- a. Local Reactions:** In placebo-controlled studies among adults, the most frequent side effect of vaccination is soreness at the vaccination site (affecting 10%–64% of subjects) that lasts  $\leq 2$  days. These local reactions typically are mild and rarely interfere with the person’s ability to conduct usual daily activities.
- b. Systemic Reactions:** Fever, malaise, myalgia, and other systemic symptoms can occur following vaccination and most often affect persons who have had no exposure to the influenza virus antigens in the vaccine. These reactions begin 6 to 12 hours after vaccination and can persist for 1–2 days. Recent placebo-controlled trials demonstrate that among older persons and healthy young adults, administration of split-virus vaccine is not associated with higher rates of systemic symptoms (e.g., fever, malaise, myalgia, and headache) when compared with placebo injections. Immediate, presumably allergic reactions (e.g., hives, angioedema, allergic asthma, and systemic anaphylaxis) rarely occur after influenza vaccination. These reactions probably result from hypersensitivity to certain vaccine components; the majority of reactions likely are caused by residual egg protein. Although current influenza vaccines contain only a limited quantity of egg protein, this protein can induce immediate hypersensitivity reactions among persons who have severe egg allergy. Persons who have experienced hives, have had swelling of the lips or tongue, or have experienced acute respiratory distress or collapse after eating eggs should consult a physician for appropriate evaluation to help determine if vaccine should be administered. Persons who have documented immunoglobulin E (IgE)–mediated hypersensitivity to eggs, including those who have had allergic responses to egg protein—also might be at increased risk for allergic reactions to influenza vaccine, persons with known allergies to eggs or who developed an allergic reaction to previous influenza vaccines will not be enrolled in this study. The tip caps of the prefilled syringes may contain natural rubber latex, which may cause allergic reactions in latex sensitive individuals. (Therefore, individuals with history of hypersensitivity to previous influenza vaccination or severe hypersensitivity to eggs/egg protein are excluded).

The adverse event profile of TIV administration in immunocompromised recipients has been comparable to that reported in healthy individuals receiving TIV. With the exception of soreness at the injection site, adverse reactions to TIV are uncommon. Minor reported side effects include: low grade fever, chills, local redness, bruising, pain, swelling at injection site, headache, malaise, and/or joint or muscle pain. Very rare side effects include severe weakness or unusual feeling in the arms or legs, high fever, and/or unusual bleeding. In some years, Guillain-Barre syndrome has been reported.

